5.3.3 Overview of Process at Treating Site

5.3.3.1 OPEN Registration

All registrations will be performed using the Oncology Patient Enrollment Network (OPEN) system. OPEN communicates automatically with the Interactive Web Response System (IWRS) which handles identifier assignments, any study randomization, and any prescribed slot assignments. If specimen analysis is required to determine eligibility, the protocol will be setup with multi-step registration.

Registration without eligibility specimen analysis:

1. Site enters registration data into OPEN during one or more steps.
2. IWRS receives data from OPEN, generates the Patient Study ID and the Universal Patient ID, both of which are sent back to OPEN.
3. IWRS sends all applicable registration data directly to Rave at the end of the final registration step.

Any data entry errors made during enrollment should be corrected in Rave.

5.3.3.2 Rave Specimen Tracking Process Steps

Step 1: Complete the **Histology and Disease** form (but do not upload reports until a specimen label can be applied to them) and the Baseline forms regarding **Prior Therapies**. Enter the initial clinical specimen data:

- **Specimen Tracking Enrollment** CRF: Enter Time Point, Specimen Category, Specimen Type, Block number, Tissue type, Surgical Path ID, and number of labels needed (include extra labels to apply to reports to be uploaded). CRF generates unique Specimen ID.

Step 2: Print labels using report in EDC and collect specimen.

- Label specimen containers and write collection date and collection time on each label. After collection, store labeled specimens as described in Section 5.3.2.
- Apply an extra specimen label to each report before scanning. Return to the **Histology and Disease** form to upload any initial Pathology, Radiology, Molecular Reports (up to 4), Surgical (or Operative) reports and Pathology Verification form (when applicable). Return to **Specimen Tracking Enrollment** CRF to upload any molecular report (one per specimen) and/or specimen specific pathology or related report (one per specimen). Uploaded reports should have protected health information (PHI) data, like name, mailing address, medical record number or social security number (SSN), redacted. Do not redact SPID, block number or relevant dates (such as collection date), and include the UPID and patient study ID on each document.

Step 3: Complete specimen data entry.

- **Specimen Transmittal** Form: Enter collection date and time and other required specimen details.

Step 4: When ready to ship, enter shipment information.

- **Shipping Status** CRF: Enter tracking number, your contact information, recipient, number of containers and ship date once for the first specimen in a shipment.
- **Copy Shipping** CRF: Select additional specimens to add to an existing shipment referenced by the tracking number.

Step 5: Print shipping list report and prepare to ship.

- Print two copies of the shipping list, one to provide in the box, the other for your own records.
- Print pathology or other required reports to include in the box. Be sure the printed copy includes the specimen label.

Step 6: Send email notification.

- For only one of the specimens in the shipment, click “Send Email Alert” checkbox on the **Shipping Status** CRF to email recipient.

Step 7: Ship the specimen(s).

5.4 Specimen Collection

5.4.1 Collection of Snap-Frozen Resection Tissue

1. Tissue should be frozen as soon as possible. Optimally, freeze within 30 minutes from resection.
2. Label a 2-mL cryovial(s) according to instructions in Section 5.3.2.
3. Using clean forceps place the tissue in a pre-chilled cryovial and freeze the vial(s) in either vapor phase liquid nitrogen, on dry ice, or by immediate placement in a -70 to -90°C or colder freezer. Keep frozen until shipment to the ETCTN Biorepository.

5.4.2 Blood Collection

5.4.2.1 Collection of Blood in Sodium Heparin Tubes for Plasma Processing

1. Label sodium heparin tube(s) according to the instructions in Section 5.3.2.
2. Collect 10 mL of whole blood in sodium heparin tube(s).
3. Process plasma by centrifuging for 10 minutes at 1,200 \times g at room temperature.
4. Using a clean transfer pipette, transfer 1 mL of plasma into each of the labeled cryovials (using the label printed from the ETCTN Specimen Tracking System or following the instructions in Section 5.3.2). Avoid picking up the blood cells when aliquoting by keeping the pipet above the cell layers and leaving a small amount of plasma in the tube. Tightly secure the cap of the vials before storage. Aliquoting and freezing of plasma specimens should be completed within 1 hour of centrifugation.
5. Store plasma cryovials upright in a specimen box or rack in an -70°C to -90°C or colder freezer prior to delivering to laboratory. Do not allow specimens to thaw after freezing.

5.4.2.2 Collection of Whole Blood in EDTA Tubes

1. Label EDTA tubes according to the instructions in Section 5.3.2.
2. Collect 5 mL blood in EDTA tube(s) and gently invert tube to mix.
3. Ship on day of collection (whenever possible) according to instructions in Section 5.6.
4. If blood cannot be shipped on the day of collection (e.g., a late scheduled collection), then refrigerate until shipment.

5.5 Shipping Specimens from Clinical Site to the ETCTN Biorepository

5.5.1 Specimen Shipping Instructions

Frozen specimens may be shipped on Monday through Thursday.

5.5.1.1 Shipping Frozen Specimens in a Single-Chamber Kit

1. Before packaging specimens, verify that each specimen is labeled according to the instructions above and that lids of all primary receptacles containing liquid are tightly sealed.
2. Place the specimens in zip-lock bags. Use a separate zip-lock bag for each specimen type

and time point.

3. Place the zip-lock bags in the biohazard envelope containing absorbent material. Expel as much air as possible and seal securely.
4. Put the secondary envelope into a Tyvek envelope. Expel as much air as possible and seal securely.
5. Place frozen specimens in the kit compartment with dry ice. Layer the bottom of the compartment with dry ice until it is approximately one-third full. Place the frozen specimens on top of the dry ice. Cover the specimens with the dry ice until the compartment is almost completely full. When packaging specimens, ensure that you leave enough room to include at least 5 pounds of dry ice in the shipment.
6. Insert a copy of the required forms into a plastic bag and place in the kit chamber.
7. Place the Styrofoam lid on top to secure specimens during shipment. Do not tape the inner chamber shut.
8. Close the outer lid of the Specimen Procurement Kit and tape it shut with durable sealing tape. Do not completely seal the container.
9. Complete a FedEx air bill and attach to top of shipping container.
10. Complete a dry ice label.
11. Attach the dry ice label and an Exempt Human Specimen sticker to the side of the shipping container.
12. Ship specimens via overnight courier to the address below. FedEx Priority Overnight is strongly recommended to prevent delays in package receipt.

5.6 Shipping Specimens from Clinical Sites to Other Laboratories

5.6.1 Shipping Blood for IUDR Incorporation to the [name] Laboratory

Fresh blood specimens should be collected and shipped Monday through Thursday.

5.6.1.1 Shipping Ambient Blood in Your Own Container

Fresh blood for 10410 must be shipped using institutional supplies. Packaging guidelines for sending blood are provided below.

1. Before packaging specimens, verify that the collection tube is labeled according to instructions in section 5.3.2.
2. Place the blood collection tube into a zip-lock bag.
3. Place zip-lock bag into a biohazard envelope with absorbent material. Expel as much air as possible and seal the envelope securely.
4. Place the biohazard envelope into a Tyvek envelope. Expel as much air as possible and seal securely.
5. Place the specimen(s) and a copy of the shipping manifest into a sturdy shipping container. In winter months, please use an insulated container and include extra insulation, such as bubble wrap, inside the shipping container to prevent specimens from freezing.
6. Close the container and tape shut.
7. Attach a shipping label to the top of the shipping container.
8. Attach an Exempt Human Specimen sticker to the side of the container.
9. Ship specimens via overnight courier to the address below. FedEx Priority Overnight is strongly recommended to prevent delays in package receipt.

5.7 Biomarker Plan

List of Biomarker Assays in Order of Priority

Priority	Biomarker Name	Assay (CLIA: Y/N)	Use in the Trial and Purpose	Specimens Tested	Collection Time Points	Mandatory or Optional	Assay Laboratory and Lab PI
Tissue-based Biomarkers							
1	IUDR Incorporation	IUDR-DNA cellular incorporation CLIA: N	Integrated To correlate %IUDR incorporation in tumor cells with IPdR PK and clinical tumor response	Surgical resection (snap frozen)	At 8-12 weeks following completion of therapy	M	Clinical Pharmacology Branch at Developmental Therapeutics Program (DTP), DCTD, National Cancer Institute (NCI) [name]. [contact]
Blood-based Biomarkers							
1	IPdR pharmacokinetics Plasma levels of IPdR, IUDR, IP and IU	PK CLIA: N	Integrated Plasma levels of IPdR, IUDR, IP and IU	Plasma (Blood collected in sodium heparin tubes)	Day 8 – Prior to the PO IPdR dose and then at 30, 60, 120, and 240 minutes following PO IPdR dose Days 21 and 35 – 1-2 hrs. following PO IPdR dose (at the time of sampling for %IUDR incorporation in circulating granulocytes)	M	Clinical Pharmacology Branch at Developmental Therapeutics Program (DTP), DCTD, National Cancer Institute (NCI) [name]. [contact]

Priority	Biomarker Name	Assay (CLIA: Y/N)	Use in the Trial and Purpose	Specimens Tested	Collection Time Points	Mandatory or Optional	Assay Laboratory and Lab PI
2	IUDR incorporation (granulocytes)	IUDR-DNA cellular incorporation CLIA: N	Integrated To correlate IUDR incorporation in granulocytes with peripheral blood counts, other systemic toxicities (CTCAE v5.0), and plasma PK obtained at the same time points.	Blood (EDTA)	Day 8 – Prior to the PO IPdR dose Days 21 and 35 – 1-2 hrs. following PO IPdR dose	M	Clinical Pharmacology Branch at Developmental Therapeutics Program (DTP), DCTD, National Cancer Institute (NCI) [name]. [contact]
3	Capecitabine pharmacokinetics Plasma levels of capecitabine, 5'-DFUR, FBAL, and 5-FU	PK CLIA: N	Exploratory Plasma levels of capecitabine, 5'-DFUR, FBAL, and 5-FU	Plasma (collected as part of the IPdR PK biomarker)	Day 8 – Prior to the PO IPdR dose and then at 30, 60, 120, and 240 minutes following PO IPdR dose Days 21 and 35 – 1-2 hrs. following PO IPdR dose (at the time of sampling for %IUDR incorporation in circulating granulocytes)	M	Clinical Pharmacology Branch at Developmental Therapeutics Program (DTP), DCTD, National Cancer Institute (NCI) [name]. [contact]

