2.5.2 Capecitabine PK

Levels of capecitabine and its metabolites will be performed on Days 8, 21, and 35 in conjunction with the IPdR PK studies, using a portion of the 10-mL blood samples described above (Section 2.5.1).

Methodologies for the capecitabine PK analyses are those detailed and reported previously (Reigner *et al.*, 2001).

2.5.3 %IUDR-DNA cellular incorporation into tumor biopsy specimen

As the %IUDR-DNA cellular incorporation in human tumor xenografts in athymic mice was linearly related to the IPdR dose when given PO QD \times 6-14 days (Kinsella *et al.*, 1994; Kinsella *et al.*, 2000b; Seo *et al.*, 2004), we will evaluate for correlation between %IUDR-DNA cellular incorporation in tumor cells obtained from the surgical resection specimen and the dose of IPdR received as a biomarker of tumor radiosensitization. Evaluation for correlation of tumor response using pCR rate and NAR score and the %IUDR-DNA cellular incorporation in tumor cells obtained from the surgical resection specimen will also be performed.

2.5.4 %IUDR-DNA cellular incorporation in peripheral (circulating) granulocytes:

%IUDR-DNA cellular incorporation in peripheral (circulating) granulocytes will be performed as a biomarker of bone marrow acute normal tissue toxicity. These analyses will be performed at three time points on study, Days 8, 21, and 35. %IUDR-DNA cellular incorporation in peripheral (circulating) granulocytes will be correlated with peripheral blood counts, other systemic toxicities (CTCAE v5.0) and plasma PK obtained at the same time points. This assay was originally developed in [name]' laboratory at NCI (Belanger *et al.*, 1986; Belanger *et al.*, 1987).

Based on our pre-clinical data regarding %IUDR-DNA cellular incorporation in bone marrow

cells harvested directly from the femurs of athymic mice and ferrets following a 14 day exposure to PO QD IPdR (Kinsella *et al.*, 1994; Kinsella *et al.*, 2000; Seo *et al.*, 2004; Seo *et al.*, 2005) we would not expect a significant correlation between the %IUDR-DNA cellular incorporation in circulating granulocytes and PK measurements, peripheral blood counts, or systemic toxicities.

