Patients will be assessed 4 weeks following completion of study treatment (Week 10 unless there were delays in therapy). This will be the final assessment for study-related toxicity. Patients will undergo surgical resection 8-12 weeks following completion of chemoRT (IPdR), and study-related response will be assessed at that time.

Regimen Description					
Agent	Premedication; Precautions	Dose	Route	Schedule	Study Length
IPdR	Take on an empty stomach, either 1 hour before or 2 hours after meals.	Dose as appropriate for the assigned dose level.	PO	QD ^A	38 days (6 weeks)
Capecitabine	Take within 30 minutes after a meal (breakfast and dinner).	825 mg/m ² ^C	PO	BID Monday morning through Friday evening on RT days ^{B,C}	
RT		1.8 Gy/fraction/day × 28 doses (50.4 Gy total dose)		5 doses per week until week 5 and 3 doses during Week 6 ^D	

^AOn the days of radiation therapy, the daily dose of IPdR will be administered within 30 min - 2 hours prior to radiation. Patients may take dose at home if the timing allows.

^BCapecitabine will be taken Monday morning through Friday evening each week of RT.

^CDosing will be with 150 mg and 500 mg tablets

^DRT will be given only Monday through Friday

QD – Once Daily, BID – Twice Daily, PO – Oral, RT – Radiation therapy

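### Capecitabine PK samples are timed only from the IPdR dose, so the same nominal Day 8 sample can lie 2.5 to 3.5 hours apart in capecitabine time

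*Combined protocol and SAP*

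**What the plan says.** Capecitabine PK has no draws of its own. Section 2.5.2 states "Levels of capecitabine and its metabolites will be performed on Days 8, 21, and 35 in conjunction with the IPdR PK studies". The assay shares the IPdR tubes, and the biomarker table in Section 5.7 describes the specimen as "Plasma (collected as part of the IPdR PK biomarker". The time points in that table are the IPdR ones. The first PK day is given as "Day 8 – Prior to the PO IPdR dose and then at 30, 60, 120, and 240 minutes following PO IPdR dose". For the two later PK days the table has a single sample, given as "Days 21 and 35 – 1-2 hrs. following PO IPdR dose". Section 5.1 and the footnotes to the Section 11 calendar use the same anchor.

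The regimen table in Section 6.1.1 sets different meal rules for the two drugs. For IPdR: "Take on an empty stomach, either 1 hour before or 2 hours after meals". For capecitabine: "Take within 30 minutes after a meal (breakfast and dinner". A footnote ties IPdR to the radiation slot: "the daily dose of IPdR will be administered within 30 min - 2 hours prior to radiation". The text available sets no order and no interval between the two drugs on PK days. In Appendix D the IPdR diary promises patients timing instructions for Days 8, 21 and 35; the capecitabine diary has no counterpart.

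Section 5.7 labels the capecitabine assay exploratory. It serves objective 1.3.2, on interactions among the two drugs and their metabolites. Section 9.5.2, where that analysis would be described, has a heading and no method.

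**The concern.** A concentration of an oral drug can be interpreted only against the time since that drug was taken. Here the clock starts at the other drug. The meal rules keep the two doses apart but allow either order, so two patients who both follow the protocol can give samples with the same label at quite different points of the capecitabine profile. If capecitabine and metabolite levels are summarised at the labelled times, samples drawn before and after the tablets are pooled.

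The stake is the usefulness of mandatory samples for objective 1.3.2. With 10 to 30 patients spread over several IPdR dose levels, avoidable timing noise matters. No dose-escalation decision depends on these data.

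**Working it through.** The plan gives no figure to reproduce, so the check is clock arithmetic followed by a calendar check.

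**Inputs.** Sample times after IPdR (Section 5.7): m = 0 (pre-dose), 30, 60, 120 and 240 min. IPdR 1 h before or 2 h after a meal; capecitabine 0 to 30 min after a meal (Section 6.1.1). Assumptions: both drugs are taken around the same meal, the 1 h and 2 h limits are met exactly, and the meal takes no time.

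**Capecitabine time with IPdR at 0.**
- Order A, IPdR before the meal: capecitabine at +1.0 to +1.5 h.
- Order B, IPdR after the meal: capecitabine at −2.0 to −1.5 h.

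**Hours since capecitabine** = m/60 − capecitabine time; a negative value means the sample precedes the dose.

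| Nominal sample | Order A | Order B |
|---|---|---|
| Pre-dose | −1.5 to −1.0 | 1.5 to 2.0 |
| 30 min | −1.0 to −0.5 | 2.0 to 2.5 |
| 60 min | −0.5 to 0.0 | 2.5 to 3.0 |
| 120 min | 0.5 to 1.0 | 3.5 to 4.0 |
| 240 min | 2.5 to 3.0 | 5.5 to 6.0 |

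**Gap between orders.** Smallest: 1.0 + 1.5 = 2.5 h. Largest: 1.5 + 2.0 = 3.5 h. It is the same at every nominal time. In order A the first two samples precede the morning capecitabine dose, and the third precedes it or at best coincides with it. Two of five are clearly post-dose.

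These two orders are not the full permitted range. IPdR follows the radiation slot, and the meal in its rule need not be breakfast. With afternoon radiation, IPdR could follow the morning capecitabine by many hours.

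**Calendar.** The Section 11 radiation days (1–5, 8–12, 15–19, 22–26, 29–33, 36–38) make 28 fractions, and 28 × 1.8 = 50.4 Gy, as planned. Day 1 is a Monday, so Day 8 is a Monday with radiation. Days 21 (3 × 7) and 35 (5 × 7) are Sundays without it. Section 6.1.3.1 limits capecitabine to radiation days, so the last scheduled dose before those samples is on Friday evening, Day 19 or Day 33. Assuming that dose is at 18:00–20:00 and Sunday IPdR at 08:00–16:00, a sample 1 to 2 h after IPdR falls between 48 + 9 − 20 = 37 h and 48 + 18 − 18 = 48 h after the last capecitabine.

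**The case against.** The strongest reply is that the needed times are already captured. The Appendix D capecitabine diary has AM and PM intake times, the IPdR diary has its own, and Section 5.3.2.1 puts the collection time on each blood label. Actual time since capecitabine can therefore be reconstructed. This stands in part: the data are not lost. But no passage says the reconstruction will be done, the diary is completed by the patient, and it has no place for meal time.

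Second, Section 2.5.1 gives the purpose of the schedule as IPdR PK comparable with the prior phase 1 trial, including any effect of capecitabine on it. For that direction an IPdR anchor is right. It does not serve the capecitabine levels drawn from the same tubes.

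Third, capecitabine PK is exploratory and last in priority among the blood biomarkers. That stands and limits the weight of the point.

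Two stronger readings are tempting, and the documents support neither.

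- A reader might turn a 3 h gap into a fold difference in concentration. An assumed half-life of 2 h gives 2^(3/2) = 2.8, and 0.5 h gives 2^(3/0.5) = 64. The documents give no half-life, and the formula ignores absorption, although the earlier sample is only 0.5 to 1 h after an oral dose taken with food. In a one-compartment oral model, concentration is proportional to e^(−k_e·t) − e^(−k_a·t), or to t·e^(−k·t) when the two rates are equal. Comparing 0.75 h with 3.75 h for those two half-lives gives ratios of about 1.6 and 13 if the absorption half-life is 0.5 h, and about 0.9 and 3.5 if it is 1 h. Even the direction is not fixed. Nor can one half-life describe capecitabine, 5'-DFUR, FBAL and 5-FU together.
- A reader might infer that dosing order would pass for a drug interaction. Nothing links order to IPdR dose level, and Section 9.5.2 specifies no comparison at matched IPdR times. Added variability is supported; a false interaction signal is not.

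**Conclusion.** The point holds as a minor one. Followed as written, the schedule gives Day 8 capecitabine samples whose nominal time does not fix their capecitabine time. Around a single meal the discrepancy is 2.5 to 3.5 h, and up to three of five samples carry no post-dose information for that morning. This rests on exact meal limits and zero meal length; longer fasting intervals or afternoon radiation could widen it. The result is extra timing variability in objective 1.3.2 and the capecitabine entry of Section 5.7. The MTD and the safety endpoints do not depend on it.

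Separately, on the nominal calendar the Day 21 and Day 35 samples fall on days with no scheduled capecitabine. The sampling days and the capecitabine schedule contradict each other for this purpose and must be reconciled.

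**What to change.** 1. On PK days, record the actual capecitabine dose time and the meal time with the PK samples, and cross-check the dose time against the diary.
2. State in Section 9.5.2 that capecitabine and its metabolites are analysed by actual time since the last capecitabine dose, not by nominal IPdR time.
3. Flag Day 8 samples drawn before that morning's capecitabine so that they are not treated as post-dose exposure.
4. Reconcile the Day 21 and Day 35 sampling days in Sections 2.5.2, 5.1, 5.7 and 11 with the capecitabine schedule in Sections 6.1.3.1 and 11, or state what a capecitabine level on those days is meant to show.

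Items 1 to 3 cost two form fields and a few lines of analysis text, with no extra samples and no change to any dose or meal rule. They make the samples interpretable but do not restore a full profile: a patient in order A still has only two clearly post-dose samples on Day 8. Item 4 needs amendment wording.

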5.8 Integrated Correlative Studies

5.8.1 IUdR Incorporation in Surgical Resection Specimen

5.8.1.1 Specimen(s) Receipt and Processing at the ETCTN Biorepository

At the time of resection, the surgical specimen will be snap-frozen by individual sites according to instruction in Section 5.4.1 and sent to the ETCTN Biorepository as soon as possible after surgical resection is performed. The ETCTN Biorepository will accession, barcode, and weigh tissue upon receipt. Frozen tissue will be stored in a liquid nitrogen vapor phase freezer until the end of the study, when they are shipped to [name] laboratory in dry ice via overnight shipping. Do not allow specimens to thaw after freezing.

Prior to distribution to [name] laboratory at the end of the study, the Biorepository will embed a piece of tissue in OCT media to section and stain for pathology QA review, including % tumor vs. stroma, % tumor vs. necrosis, and confirming concordance with the institutional diagnosis.

5.8.2 IPdR and Capecitabine PK

5.8.2.1 Specimen(s) Receipt and Processing at the ETCTN Biorepository

Upon receipt, the ETCTN Biorepository will accession, barcode, and bank frozen plasma aliquots in a -80°C freezer until distribution. Plasma samples for each patient should be batched and sent to [name] laboratory as soon as the Day 35 sample is received at the Biorepository.

